5.3 SBRT Treatment Delivery

All patients should receive 5 fractions of 800 cGy over a five-day period (See Section 6 for dose modification). Ideally all 5 fractions should be delivered Monday through Friday, however it may be delivered over two weeks.

Within three weeks of the initial treatment planning imaging study, SBRT will be administered using image-guidance. This protocol allows conventional linear accelerators and specialized linear accelerators with image guidance (e.g. Novalis, Trilogy, Synergy, Artiste) capable of conformal dose delivery and IMRT. Specialized accelerators (e.g. Cyberknife or Tomotherapy) are also allowed.

During treatment, real time cone beam CT images of the patient's body site of interest will be obtained. Cone beam CT scan will be obtained immediately prior to treatment and will be repeated until the treatment shift, required to align the CT planning scan and the cone beam CT scan performed on the day of treatment, is within 2 mm.

Anesthesia or sedation may be required in certain patients, such as very young patients, to prevent movement during simulation and daily treatments. Anesthesia will be delivered by a dedicated pediatric anesthesiologist.

5.4 General Concomitant Medication and Supportive Care Guidelines

There are no known potential interactions between SBRT and concomitant medications.

5.5 Duration of Therapy

In the absence of treatment delays due to adverse event(s), treatment may continue for 2 weeks or until one of the following criteria applies:

- Disease progression,
- Intercurrent illness that prevents further administration of treatment,
- Unacceptable adverse event(s),
- Patient or parent/guardian (for minors) decides to withdraw from the study, or
- General or specific changes in the patient's condition render the patient unacceptable for further treatment in the judgment of the investigator.

5.6 Post-SBRT Follow-up

Subsequent to SBRT, patients will be monitored as follows:

5.6.1 4 Weeks Post-SBRT

5.6.2 At 3, 6, 9, 12, 18, 24, 30, and 36 months Post-SBRT

5.7 Duration of Follow-Up

It is anticipated the patients that remain on-study will be followed for 3 years.

Patients will remain enrolled on this protocol until there is evidence that their disease has progressed either locally or distally, at which case they will be removed from the protocol and be followed for survival only. Patients removed from study for unacceptable adverse events will be followed per protocol until resolution or stabilization of the adverse event and then followed for survival only.

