13.1.2 Analysis plan for primary endpoint

The primary endpoint of this study will be local control at 6 months of the patient treated with SBRT. Given the inherent difficulties in defining response in bony lesions after radiotherapy by RECIST 1.1 criteria, local control at the radiated site will be defined as the absence of progression of disease as defined in Section 9.1.4.1. Thus, CR and SD will constitute local control. Local control assessment will start at one month following completion of protocol treatment and continuous assessment will be pursued during the follow-up period. The reference response probability for comparison will be 70%. This is based on the study by Kepka et al. (31)

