13.2 Sample Size/Accrual Rate

The primary endpoint of this trial is to estimate the local control of SBRT at 6 months. We anticipate that the local control rate will be roughly 90% as opposed to a 70% historical response with conventional moderate dose radiation. With 20 subjects participated, we will be able to estimate the local control rate to within 20% (i.e., maximum width of the 90% confidence interval reached is when the observed rate is 50%). If we observe a 6-month local control rate of 90%, we will be 90% certain that the true rate is greater than 70%. The associated exact 90% confidence interval will be (0.72, 0.98).

Using a Simon optimal two-stage design with a type I error of 10% and a type II error of 20%, the first stage would consist of 6 patients. A responder is considered to have local disease control at 6 months. If 4 or fewer patients respond, the study would terminate after the first stage. Otherwise, accrual would continue to a total of 20 patients. If 17 or more patients respond at the end of the second stage, the regimen with SBRT is considered promising (i.e., local control at 6 months is greater than 70%). This design has a 58% chance of early stopping when the true probability of response is 70% (the null hypothesis) and 11% chance of early stopping when the true probability of response is 90%.

The goal of enrollment is 20 patients. Based on the current institutional referral base, we expect that 12 patients will be eligible each year. Of these patients, we expect that two thirds will enroll on protocol. With this projection, we plan to complete accrual to the study in 3 years.

The proportion of patients with local control at six months will be reported with an exact binomial 90% confidence interval.

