13.4 Reporting and Exclusions

13.4.1 Evaluation of toxicity. All patients will be evaluable for toxicity from the time of their first treatment with SBRT.

13.4.2 Evaluation of response. All patients included in the study must be assessed for response to treatment, even if there are major protocol treatment deviations. Each patient will be assigned one of the following categories: 1) complete response, 2) stable disease, 3) progressive disease, 4) early death from malignant disease (defined as death prior to first evaluation after completion of SBRT), 5) early death from toxicity, 6) early death because of other cause, or 9) unknown (not assessable, insufficient data). [Note: By arbitrary convention, category 9 usually designates the “unknown” status of any type of data in a clinical database.]

All of the patients who were enrolled on the trial should be included in the main analysis of local control.

All conclusions should be based on all enrolled subjects. Sub-analyses may then be performed on the basis of a subset of patients, excluding those for whom major protocol deviations have been identified (e.g., early death due to other reasons, early discontinuation of treatment, major protocol violations, etc.). However, these sub-analyses may not serve as the basis for drawing conclusions concerning treatment efficacy, and the reasons for excluding patients from the analysis should be clearly reported. The reason for performing subset analyses would be to generate hypotheses for future prospective clinical trials.

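### Section 5.7 ends required treated-site imaging at distant progression, so the 6-month local control status can be lost, and no explicit rule scores such patients in the 5-of-6 and 17-of-20 decisions

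*Combined protocol and SAP*

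**What the plan says.** Section 5.7 plans three years of follow-up, but a patient stays on protocol only until disease has "progressed either locally or distally, at which case they will be removed from the protocol and be followed for survival only". Section 5.8 also removes patients for any criterion in 5.5. That list includes disease progression and does not separate local from distant.

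The endpoint concerns the treated site alone. In 13.1.2, "local control at the radiated site will be defined as the absence of progression of disease as defined in Section 9.1.4.1", with CR and SD counting as control, and "continuous assessment will be pursued during the follow-up period". Section 13.2 adds: "A responder is considered to have local disease control at 6 months". The decision rule there is to stop with 4 or fewer of the first 6, and to call the regimen promising with 17 or more of 20. The Study Calendar (Section 8) schedules a treated-site CT at 3 and 6 months; follow-up MRI and PET are optional.

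On the analysis set, 13.4.2 says "All patients included in the study must be assessed for response to treatment, even if there are major protocol treatment deviations" and "All of the patients who were enrolled on the trial should be included in the main analysis of local control". Its categories include CR, SD and PD, three kinds of early death (the first being "early death from malignant disease (defined as death prior to first evaluation after completion of SBRT") and category 9, "unknown (not assessable, insufficient data". None carries a time point.

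**The concern.** Distant progression is not part of the primary endpoint, yet it ends the follow-up that measures it. A patient with local progression before removal can already be scored as a failure. The gap is the patient with distant-only progression before month 6. That patient must be in the analysis, but the 6-month status may never be observed.

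With 20 patients and a cut-off of 17, the scoring of one or two such patients can decide the result. If two of the first six are unscanned and the other four are controlled, the trial stops when the two count as failures (4 of 6) and continues when they count as controlled (6 of 6). That choice should not be left until the data are known.

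**Working it through.** **The texts side by side.** Three readings of an unscanned patient can be drawn:

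- *Not controlled.* In 13.1.2 only CR and SD are control. Section 13.4.2 keeps unknown and early death apart from CR and SD, over all enrolled. Section 13.2 ties response to control at 6 months. This fits the text best, but it is implied.
- *Controlled by default.* Section 9.1.4.1 makes SD anything that is neither CR nor PD, and 9.1.6 treats a lesion as controlled unless progression criteria are met.
- *Excluded.* Section 9.1.1 limits response evaluability to patients whose disease was re-evaluated. The cut-offs of 5 of 6 and 17 of 20 then have no defined denominator.

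Because the categories carry no time point, a patient stable at 3 months and then removed could be entered as category 2 or as category 9.

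**The plan's own figures.** Inputs from 13.2: p0 = 0.70, p1 = 0.90, 6 patients then 14 more.

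Early stopping = P(X1 ≤ 4 | 6, p) = 0.580 at 0.70 and 0.114 at 0.90 (stated 58% and 11%).

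P(promising) = P(X1 = 5)·P(X2 ≥ 12 | 14) + P(X1 = 6)·P(X2 ≥ 11 | 14)

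- p = 0.70: 0.302526 × 0.160836 + 0.117649 × 0.355167 = 0.048657 + 0.041785 = 0.0904
- p = 0.90: 0.354294 × 0.841640 + 0.531441 × 0.955867 = 0.298188 + 0.507987 = 0.8062

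The design reproduces, with type I error 9.0% and power 80.6%. Both assume a known 6-month status for every patient.

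**Adding loss.** Assume that a share d is lost before the 6-month scan, independently of local control. The documents give no d; 5, 10 and 20% are illustrations. The response probability p is replaced by:

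- lost = not controlled: p(1 − d)
- lost = controlled, no local failure documented before removal: p + (1 − p)d
- lost = controlled, half of those failures already documented (an assumption): p + (1 − p)d/2

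| | d = 0 | 5% | 10% | 20% |
|---|---|---|---|---|
| Not controlled, p = 0.90: effective p | 0.900 | 0.855 | 0.810 | 0.720 |
| Power | 80.6% | 60.4% | 40.0% | 12.4% |
| Stage-1 stopping | 11.4% | 21.2% | 32.0% | 53.6% |
| Not controlled, p = 0.70: type I error | 9.0% | 4.9% | 2.5% | 0.5% |
| Controlled, none documented, p = 0.70: type I error | 9.0% | 11.5% | 14.5% | 22.1% |
| Controlled, half documented, p = 0.70: type I error | 9.0% | 10.2% | 11.5% | 14.5% |

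Type I error passes the planned 10% at d = 2.05% with none documented, and at d = 4.1% with half documented.

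**By count.** With exactly 1, 2, 3 or 4 of 20 lost and scored as failures, power at 90% control is 63, 38, 13 and 0%. With four lost, at most 16 can respond.

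**If loss is not independent.** Suppose local failures are twice as likely to be lost, at the same overall d. Among controlled patients the loss share is then d/(0.9 + 2 × 0.1) = d/1.1. With lost = not controlled, power is 62, 44 and 16% at d = 5, 10 and 20%, much as before.

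**The case against.** The strongest reply is that the protocol already implies a rule: only CR and SD are control, unknown is a separate category, and all enrolled patients are in the denominator. Default control would leave category 9 nearly empty, which fits 13.4.2 poorly. This largely stands. A reader might infer that nothing in the documents bears on the scoring, but that goes too far. What is missing is an explicit rule and a time point for SD.

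A reader might also infer that 5.7 and 13.4.2 flatly contradict each other, or that 5.7 forbids the scan. Neither is supported. Category 9 lets a removed patient be classified, and 5.7 only ends the requirement to image. A routine-care scan may exist, though no text provides for its use. The tension is with the instruction to assess everyone and with the 6-month time point.

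Third, the larger type I error figures assume that no lost patient had a documented local failure. The required 3-month CT will catch some, and those patients are failures under any rule. This stands, so the 11.5/14.5/22.1% row is the upper end under independent loss. It also rests on the weaker reading.

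Last, Sections 5.6.1 and 5.6.2 show no content in the text available for review, so some follow-up detail may not be visible. The Study Calendar is visible and makes no exception to 5.7. This lowers certainty only slightly. Kaplan-Meier locoregional control (13.3.2) does not fill the gap: it is secondary, while the primary analysis is a binomial proportion.

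**Conclusion.** The point holds and should be settled before either decision count is made. As written, 5.7 stops requiring the primary-endpoint scan in patients whose progression is only outside the treated site, and no visible text restores it. Their place in the two decisions is implied but not stated, and an earlier stable scan may or may not count as SD.

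Under the better-supported reading the cost is power and early stopping, not false positives: 60, 40 or 12% power and 21, 32 or 54% stage-1 stopping at d = 5, 10 or 20%. These values rest on an assumed d and on independence from local control. The case for change rests on the follow-up rule and the unstated scoring, not on any particular d.

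A reader might infer that the trial's type I error exceeds 10%, or that the sample size is wrong. The documents support neither. Inflation needs the default-control reading and enough undocumented local failures, and the two-stage design is correct for complete data.

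**What to change.** Amend 5.7, and align 5.8, so that progression outside the treated site(s) does not end the already scheduled treated-site CTs through the 6-month visit. Record the type and start date of any new anticancer therapy; 3.2.4 already allows such therapy at progression.

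In 13.1.2 and 13.4.2, state that:

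- local control is judged at the 6-month assessment in all enrolled patients;
- the evaluability definition in 9.1.1 does not restrict this analysis;
- a patient with no 6-month treated-site assessment counts as not controlled at both decision points, whatever the 13.4.2 category.

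Report the number of such patients, with a sensitivity analysis in all enrolled patients under the opposite rule. The sponsor could make the opposite rule primary if it says so in advance and shows the type I error.

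The change is to wording. It costs up to two already scheduled CTs and visits (3 and 6 months) per affected patient. Local control will sometimes be read after new systemic therapy, which is why the start date is needed. Residual unknowns still cost power: at d = 2% the effective rate is 0.90 × 0.98 = 0.882 and power is 73%. Continued toxicity visits are not needed for the primary endpoint and are not part of this change.

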5.8 Criteria for Removal from Study

Patients will be removed from study when any of the criteria listed in Section 5.5 applies. The reason for study removal and the date the patient was removed must be documented in the Case Report Form.

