7.3 Recording and Reporting of Adverse Events

Participating investigators will assess the occurrence of AEs and SAEs at all participant evaluation time points during the study.

All AEs and SAEs whether reported by the participant, discovered during questioning, directly observed, or detected by physical examination, laboratory test or other means, will be recorded in the participant's medical record. Low grade toxicities are to be expected given the disease profile. Any toxicity below CTCAE v4.0 grade 3 will not be reported on the Master AE Log or Case Report Forms. However, this information will be monitored and retained in patient charts.

Hematologic toxicity will be assessed and monitored but not reported.

Hospitalization events occur within this patient population. Hospitalizations that occur greater than 30 days from completion of SBRT and that are not attributable to research intervention will be recorded on the Master AE Log and reported at the time of continuing review and SMC monitoring.

These parameters are drafted in accordance with CFR21, though provide realistic expectations based on the sickness of this patient population.

The descriptions and grading scales found in the revised NCI Common Terminology Criteria for Adverse Events (CTCAE) version 4.0 will be utilized for AE reporting. All appropriate treatment areas should have access to a copy of the CTCAE version 4.0. A copy of the CTCAE version 4.0 can be downloaded from the CTEP website at: http://ctep.cancer.gov/protocolDevelopment/electronic_applications/ctc.htm.

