9.1.1 Definitions

Evaluable for toxicity. All patients will be evaluable for toxicity from the time of their first treatment with SBRT.

Evaluable for objective response. Only those patients who have measurable disease present at baseline, have completed all fractions of SBRT, and have had their disease re-evaluated will be considered evaluable for response. These patients will have their response classified according to the definitions stated below. (Note: Patients who exhibit objective disease progression prior to the end of SBRT will also be considered evaluable.) Evaluable patients will also be those who received the protocol-specified dose.

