13.3 Analysis of Secondary Endpoints

13.3.1 Definition of secondary outcomes/endpoints:

- To describe the toxicity of SBRT delivered to a dose of 4000 cGy in 5 fractions of 800 cGy each for the population enrolled using grading with CTCAE v. 4.0
- The clinical response rate of each lesion will be assessed by serial CT assessment (FDG-PET/CT is optional for assessment) and defined by criteria as defined above. The absence of progression will constitute a response. Therefore, lesionspecific CR or SD will be measured as a response.
- To assess long-term clinical outcomes of this patient population after completion of SBRT by measuring relapse-free survival and overall survival. Relapse-free survival will be measured from time of enrollment to date of disease progression or death. Patients who are lost to follow-up will be censored for determination of

progression-free survival on the date of their last evaluation. Overall survival is defined as time from enrollment to death due to any cause.

- To assess quality of life following completion of SBRT using pre- and post-SBRT completion of the Brief Pain Inventory form and 10 point Visual Analog Scale which will be filled out by the patient at the treatment response intervals outlined above.

13.3.2 Analysis plan for secondary endpoints:

- Toxicities will be graded and tabulated at the time of each follow-up assessment. The proportion of toxicities by type and grade will be reported with exact 95% confidence intervals.
- Each metastatic lesion will be considered a target lesion and independently evaluated for response. The proportion of these lesions that have a stable or better response and the intra-cluster correlation will be estimated with an intercept only generalized estimating equation (GEE) regression. This will be estimated directly with SAS Genmod by specifying binomial variation, the identity link function, and an exchangeable correlation structure.
- Hazard rate estimates and 95% confidence intervals as well as Kaplan-Meier (KM) estimates will be used to summarize survival (OS), progression free survival (PFS), time to progression (TTP) and locoregional control (LRC) functions over time. The median OS, PFS, TTP and LRC will be reported. Cox proportional hazards models will be used to evaluate the impact of key covariates on these endpoints as the sample size permits.

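### Scheduled toxicity assessment stops at any local or distant progression, yet all treated patients stay evaluable for toxicity and the analysis makes no allowance for the incomplete follow-up

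*Combined protocol and SAP*

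**What the plan says.** **Follow-up.** Section 5.7 plans three years: "It is anticipated the patients that remain on-study will be followed for 3 years". Patients stay enrolled "until there is evidence that their disease has progressed either locally or distally", after which "they will be removed from the protocol and be followed for survival only". Section 5.8 adds that "Patients will be removed from study when any of the criteria listed in Section 5.5 applies", and disease progression is on the Section 5.5 list. The one stated exception concerns a different reason for leaving: "Patients removed from study for unacceptable adverse events will be followed per protocol until resolution or stabilization of the adverse event".

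**Assessment.** Section 7.3 says "Participating investigators will assess the occurrence of AEs and SAEs at all participant evaluation time points during the study". The study calendar (Section 8) schedules toxicity assessment during SBRT, at 4 weeks, and at 3, 6, 9, 12, 18, 24, 30 and 36 months. Its only other follow-up entry is for survival.

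**Analysis.** Section 9.1.1 states "All patients will be evaluable for toxicity from the time of their first treatment with SBRT", and Section 13.4.1 repeats it. Section 13.3.2 tabulates toxicities at each follow-up assessment and then says "The proportion of toxicities by type and grade will be reported with exact 95% confidence intervals". It gives no censoring, person-time or competing-risk method for toxicity and no denominator for each time point.

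**Serious events.** Section 7.3.1.2 requires every SAE to be collected regardless of causality, and fatal events to be reported within 24 hours of the site learning of them. It does not say how long this duty lasts after a patient is removed.

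**The concern.** A new distant lesion carries no information about injury at the irradiated bone, yet it ends the visits at which such injury would be looked for. A patient with a new distant lesion at month 4 and a Grade 3 event at a treated site at month 10 has no scheduled visit at which that event is recorded, but is still evaluable for toxicity.

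An ongoing adverse event is also handled by the reason for leaving. If the event caused removal, it is followed to resolution or stabilization. If progression caused removal, Section 5.7 makes no such provision.

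The protocol itself says that complication rates for this treatment are hard to predict (Section 7.1) and that it is not well studied in children (Protocol Summary). The toxicity table is therefore a main product of the trial. As the plan stands, its later part describes mostly patients who have not progressed.

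**Working it through.** **1. Text check.** Read together, Sections 5.7, 5.8, 7.3 and the calendar stop scheduled toxicity assessment at progression. Sections 9.1.1 and 13.4.1 set a start for evaluability and no end. Section 13.3.2 gives a crude proportion. Two readings of the denominator follow:

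- *All treated patients.* Unobserved time after progression counts as event-free, so the proportion is a lower bound.
- *Patients assessed at each visit.* The later rows describe patients still progression-free, which is selective loss.

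The plan does not say which is meant, and neither reading deals with the gap.

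**2. How many toxicity visits would take place.** The plan has no figure to reproduce: the documents give no PFS, OS or late-toxicity rate. I assume exponential curves and take the 4-week visit as month 1.

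- Visit times t = 1, 3, 6, 9, 12, 18, 24, 30, 36 months.
- Expected visits made per patient = sum of 0.5^(t / median PFS).
- Expected visits due while alive = sum of 0.5^(t / median OS).
- Share made = the first divided by the second.

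| Median PFS / OS (months) | Made | Due in living patients | Share, all visits | Share, after month 6 |
|---|---|---|---|---|
| 4 / 24 | 2.19 | 6.08 | 36% | 0.40 / 3.35 = 12% |
| 6 / 18 | 2.94 | 5.45 | 54% | 0.84 / 2.80 = 30% |
| 12 / 18 | 4.49 | 5.45 | 82% | 2.00 / 2.80 = 71% |

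In the middle case, at 12 months 0.5^(12/6) = 25% of patients are still on toxicity follow-up, while 0.5^(12/18) = 63% are alive.

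**3. From visits to events, as an illustration only.** Missed visits are not bias, and the step from one to the other needs a toxicity rate that must also be assumed. Take constant, independent hazards, a 36-month toxicity risk of 20% if nobody died, median time to progression 12 months, median survival after progression 12 months, and nothing captured after progression (no SAE reports either).

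- Toxicity hazard a = -ln(0.8)/36 = 0.00620; progression hazard b = ln(2)/12 = 0.05776; a + b = 0.06396.
- Seen before progression: a/(a + b) × [1 - exp(-36(a + b))] = 0.0969 × 0.900 = 8.7%.
- Occurring before death: the integral from 0 to 36 of a·exp(-at)·S(t), with S(t) = exp(-bt)(1 + bt), = 14.6%.
- Captured share: 8.7 / 14.6 = 60%, or about 1.7 of 2.9 affected patients in 20.

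Over assumed toxicity risks of 10% to 30%, with the same survival after progression, the captured share is about 40-41% at a 6-month median time to progression, 59-60% at 12 months and 76-77% at 24 months.

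**4. Safety rule.** Section 11.2 describes toxicity monitoring as continuous. After progression no scheduled visit feeds the rule; an event reaches it only if reported as an SAE. The rule can act only during accrual: Section 13.2 expects 12 × 2/3 = 8 patients a year, so 20/8 = 2.5 years, with 3 years planned.

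**The case against.** A reader might infer that nothing but survival is recorded after progression, that the safety rule never sees later events, and that the reported rates are certainly too low. The documents do not support statements that strong.

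- **SAEs.** Section 7.3.1.2 asks for all SAEs with no stated end, and Section 7.3 logs unrelated hospitalizations more than 30 days after SBRT. A serious fracture or myelitis could be reported this way. This stands in part: the duty sits in tension with the survival-only wording of Section 5.7, schedules no visit to find events, and does not cover non-serious Grade 3 events.
- **Denominator.** Tabulation at each assessment may mean that only patients seen at that visit are counted. This stands: dilution is one of two possible readings, and the other has a different defect.
- **Timing.** Section 7.1 calls only growth delay or arrest a late effect. It gives no timing for fracture, and myelitis appears only as a dose-constraint endpoint. This stands, so the point does not rest on those events being late. Height is also measured only pre-study, so longer toxicity follow-up would not by itself detect growth arrest.
- **Size.** The visit shares rest on assumed curves and are not a measure of bias. This stands. Toxicity before progression is unaffected, and deaths are still captured.
- **Safety rule.** Many later events would fall after accrual under any follow-up scheme. This stands and limits the effect on Section 11.2.
- **Disclosure.** The Protocol Summary concedes that late effects cannot be assessed, but it refers to effects at 10 years or more, not to loss within the planned 36 months.
- **Attribution.** Later therapy blurs cause. That is true, but progression-free patients may already receive chemotherapy from 2 weeks after SBRT with toxicity still collected.

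**Conclusion.** The concern holds in this form: scheduled ascertainment of Grade 3+ toxicity stops at any progression, and the analysis has no method for the follow-up that is lost. The crude proportion is a lower bound if all treated patients form the denominator, and subject to selective loss if only those assessed do. SAE reporting gives partial and unclear cover. The size of the understatement cannot be computed from the documents. Under the assumed curves, between 36% and 82% of the toxicity visits due in living patients would occur, and between 12% and 71% of those after month 6. This affects a secondary objective and the completeness of safety monitoring. It contradicts no stated figure. It should be corrected, because the remedy changes only data collection and reporting.

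**What to change.** **Sections 5.7 and 8, reconciled with 7.3.1.2.** State that progression does not end collection of Grade 3-5 non-hematologic toxicity at or near irradiated sites. Record it, with attribution, at the scheduled time points to 36 months or death, at clinic visits or survival follow-up contacts. Continue to collect data on ongoing events whatever the reason for removal. State how long the SAE duty lasts after removal.

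**Section 13.3.2.** Name the denominator. Report late Grade 3-5 toxicity with the number at risk at each time point and as cumulative incidence with death as a competing event, beside the crude proportion.

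**Cost.** There is modest extra data collection and some CRF wording. The documents do not describe how survival status is obtained, so some contacts may have to be added, and grading some events may need an examination or imaging report. Attribution becomes noisier once later therapy starts; the five-level scale in Section 7.2.4 records that judgment but does not resolve it. With 20 patients the cumulative incidence will be imprecise, which is why the crude proportion and numbers at risk should stand beside it.
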